Malignant pleural effusion (MPE) is common, and is estimated to affect up to a half of patients with malignancy, either at the time or during subsequent clinical course after the diagnosis of malignancy. Lung cancer is the most common cause of MPE, followed by breast cancer, lymphoma, unknown primary genitourinary and gastrointestinal carcinoma. Pleural involvement indicates dissemination of malignancy and suggests a poorer prognosis and the median survival rate ranges from 3 to 12 months, with lung cancer showing the shortest survival among Caucasian cohorts. Patients with MPE frequently suffer from effusion related symptoms requiring therapeutic drainage. Conventionally, the options of therapeutic drainage of MPE include needle aspiration, and intercostal drain insertion with or without chemical pleurodesis. Needle aspiration allows quick relief of effusion and symptoms, though the volume of pleural effusion being aspirated with each attempt of needle puncture is limited to 1-1.5 litres, and repeated puncture involves risks of complications. Intercostal drain insertion will allow gradual drainage of large pleural effusion over days, but the shortcomings being the long hospitalization of at least a week, and the presence of trapped lung would preclude chemical pleurodesis for definitive fluid control. Up to 40% of MPE patients still require repeated pleural drainage procedure, even after Talc chemical pleurodesis. The much longer hospitalization period is considered unfavourable for patients with limited lifespan in terms of weeks or a few months, who would spend more time with their family. In recent few years, indwelling pleural catheter (IPC) has provided a relatively novel option of palliative MPE drainage, on an ambulatory out-patient setting. IPC has been reported to be cost-effective, in particular for patients with survival of less than 14 weeks. With the limited time span, it is important to balance between the aim of symptomatic relief and maintaining patient's quality of life. Invasive procedures and prolonged hospitalisation can cause great distress to patients. Predicted survival of patients with MPE would be important in informing the most suitable method for relieving MPE. Previous studies have identified relevant factors on prediction of survival in patients with malignant pleural effusion but so far, there is no data for Chinese patients. The LENT scoring system (pleural fluid lactate dehydrogenase, Eastern Cooperative Oncology Group performance score, neutrophil -to-lymphocyte ratio and tumour type) is a new validated prognostic score in malignant pleural effusion.

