
This study aims to identify prognostic factors and evaluate the use of LENT score in Chinese patients with malignant pleural effusion that can subsequently shed light on the treatment approach.

Objectives

To investigate the prognostic factors predicting survivals and need of repeated pleural drainage in patients with malignant pleural effusion

Trial Design:

Longitudinal cohort study, observational

Study investigations:

Patients are retrospectively identified from Hospital Authority Clinical Management System. Clinical Data Analysis and Reporting System (CDARS) will be used to retrieve the list of adult subjects (age 18 or above) having been investigated at Queen Mary Hospital, with the diagnosis of malignant pleural effusion from 2010 and onwards. Upon commencement of the current study, patients newly diagnosed to have malignant pleural effusion, who are under the care of Department of Medicine, will also be prospectively recruited and informed consent will be obtained for use of their data. Their baseline demographic data, blood test results and pleural fluid results will be retrieved/ collected, and data on their subsequent clinical course will also be collected for study purpose. The blood tests and pleural fluid workups are all clinical routine investigations, and study only involves data utilization. The study does not involve any additional interventions for the subjects.

The study does not involve retrieval of sensitive data, nor any active interventions on study subjects. Data will be anonymous and the individuals will not be identifiable. Any database collected will be encrypted. Therefore, for retrospectively found subjects, irrespective of their status at the study time (alive or dead), informed consent will not be actively pursued.

The following data will be collected:

1. Baseline characteristics:

Patient variables including age, performance status and other co-morbidities will be collected at the start of study, and at the time of diagnosis of MPE.

2. Blood tests data:

Variables at initial diagnosis will be collected including complete blood count, inflammatory variable such as C-reactive protein, lactic dehydrogenase, protein and albumin levels.

3. Pleural fluid data:

Variables including pH, glucose, lactic dehydrogenase and protein level will be collected.

Outcomes:

1. Primary outcome/endpoints:

Rate of fluid recurrence requiring invasive pleural interventions

2. Secondary endpoints:

Survival

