Need of definitive fluid control measure

Complications of pleural interventions

Statistical analysis

Multivariable Cox model and linear regression will be undertaken to identify factors predictive of survival and need of pleural tapping. A modified LENT score (pleural fluid lactate dehydrogenase, Eastern Cooperative Oncology Group performance score, neutrophil -to-lymphocyte ratio and tumour type) will be investigated for risk stratification using the Kaplan Meier survival curve and Receiver Operating Characteristic curve analysis.

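### The LENT evaluation plans ROC analysis and Kaplan-Meier curves by group but no comparison of observed with predicted survival, so miscalibration in Chinese patients could go unremarked

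*Combined protocol and SAP*

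**What the plan says.** The score evaluation is a single sentence in the Statistical analysis section. It concerns "A modified LENT score (pleural fluid lactate dehydrogenase, Eastern Cooperative Oncology Group performance score, neutrophil -to-lymphocyte ratio and tumour type", and the plan is that this score "will be investigated for risk stratification using the Kaplan Meier survival curve and Receiver Operating Characteristic curve analysis". The modification, the cut-points and the risk groups are not defined. The sentence before it reads "Multivariable Cox model and linear regression will be undertaken to identify factors predictive of survival and need of pleural tapping"; those models look for predictive factors and are not linked to checking the score's predictions. No calibration plot, calibration slope, observed-to-expected ratio or other comparison of observed with predicted survival appears anywhere in the document.

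The purpose is stated earlier. The background says "Predicted survival of patients with MPE would be important in informing the most suitable method for relieving MPE" and, on prognostic factors for survival, that "there is no data for Chinese patients". It also notes that "IPC has been reported to be cost-effective, in particular for patients with survival of less than 14 weeks". The aim, stated just before the Objectives, is to "evaluate the use of LENT score in Chinese patients with malignant pleural effusion that can subsequently shed light on the treatment approach". Survival is a secondary endpoint.

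**The concern.** A prognostic score has two separate properties. Discrimination is whether it puts patients in the right order. Calibration is whether the survival it attaches to each group is right. When a validated score is taken to a population in which it has not been studied, ranking often carries over while absolute survival does not, for example because case mix or treatment differs.

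The background's reason for interest in LENT is absolute: how long a patient is likely to live bears on which drainage method suits. The study's reason for testing LENT is transport to Chinese patients. Whether predicted survival carries over is therefore close to the centre of the aim, and the plan contains no step that asks it. A reassuring AUC and well-separated curves could be reported without anyone remarking that survival in each group differs materially from what the score implies.

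**Working it through.** **No figure to reproduce.** The documents give no sample size, event count, AUC target or predicted survival by LENT group. The check below shows how each planned analysis responds to a calibration error.

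**Inputs**
- From the background: the 14-week survival figure, and a 3 to 12 month range of median survival for malignant pleural effusion in general ("the median survival rate ranges from 3 to 12 months"). That range is not a set of LENT predictions.
- Assumed: exponential survival; three risk groups with shares 30/40/30%; predicted medians of 12, 6 and 3 months; true survival time equal to k times predicted in every group.

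**Step 1: deaths by 14 weeks.** 14 weeks = 98 days ÷ (365.25/12) = 3.22 months. P(death by 14 weeks) = 1 − 2^(−3.22/median).
- Predicted (k = 1): 17.0%, 31.1%, 52.5%.
- True survival doubled (k = 2; medians 24, 12, 6 months): 8.9%, 17.0%, 31.1%.
- True survival halved (k = 0.5; medians 6, 3, 1.5 months): 31.1%, 52.5%, 77.4%.

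With k = 2 the high-risk group's 14-week mortality is overstated by 52.5 − 31.1 = 21 percentage points.

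**Step 2: concordance (uncensored, ties counted 0.5).** For two groups, the chance that the higher-risk patient dies first is λ_high/(λ_high + λ_low): 2/3 for adjacent groups and 4/5 for low against high. The pair weights are 0.24, 0.24 and 0.18, with 0.34 tied. C = 0.24 × 2/3 + 0.24 × 2/3 + 0.18 × 0.8 + 0.34 × 0.5 = 0.634. The factor k cancels, so C is the same however wrong the predicted survival is.

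**Step 3: AUC at 14 weeks.** Let a = share × P(death) and b = share − a. AUC = [a_high(b_low + b_mid + ½b_high) + a_mid(b_low + ½b_mid) + ½a_low·b_low] / (Σa·Σb).
- k = 1: a = 0.0510, 0.1244, 0.1575; b = 0.2490, 0.2756, 0.1425. AUC = 0.1483/(0.3329 × 0.6671) = 0.668.
- k = 2: a = 0.0267, 0.0680, 0.0933; b = 0.2733, 0.3320, 0.2067. AUC = 0.0996/(0.1880 × 0.8120) = 0.653.
- k = 0.5: the same formula gives 0.696.

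**Step 4: observed-to-expected (O/E) deaths by 14 weeks.** Expected = 0.333. O/E = 0.188/0.333 = 0.56 for k = 2, and 0.536/0.333 = 1.61 for k = 0.5.

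| True survival ÷ predicted | Concordance | AUC, 14 weeks | O/E, 14 weeks |
|---|---|---|---|
| 0.5 | 0.634 | 0.696 | 1.61 |
| 1 | 0.634 | 0.668 | 1.00 |
| 2 | 0.634 | 0.653 | 0.56 |

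The AUC is highest in the row where deaths exceed prediction by 61%.

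**Step 5: other assumed shares.** With shares of 20/50/30% and k = 0.5, 1, 1.5 and 2, a simulation of 200,000 patients gave AUC 0.677, 0.648, 0.642 and 0.636, and O/E 1.60, 1.00, 0.72 and 0.57. The pattern is the same.

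**Step 6: what Kaplan-Meier would show.** With k = 2 the high-risk curve would show a median near 6 months and about 31% dead by 14 weeks. These are the correct absolute figures. Only the predicted 3 months and 52% to set beside them are missing from the plan.

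**The case against.** The strongest reply is that Kaplan-Meier curves are not a ranking measure. Drawn by score group, they estimate absolute survival in this cohort, at 14 weeks and elsewhere, and that is the treatment-relevant information a clinician would want. The plan does not say that imported survival figures will be attached to the groups, and it limits the score analysis to risk stratification, for which ROC and group curves are ordinary tools. This largely stands. A reader might infer that both planned analyses look only at ranking, and the documents do not support that: the observed half of a calibration check will already exist. The comparison is what is absent.

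A second reply is that the score is modified in an undefined way. If its cut-points or weights are re-derived here, no published group survival matches it, and external calibration has nothing to test. This stands too, and it shapes the fix: the form of validation depends on which score is evaluated. It does not remove the gap, because a re-derived score needs internal validation and the plan names none.

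Third, the 14-week figure is background on the cost-effectiveness of one drainage option. It is not a study cut-off, and it is used here only as a convenient time point.

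**Conclusion.** The point holds in limited form. The plan assesses discrimination and observed survival by group but plans no comparison with predicted survival, so a score that ranks well and predicts wrongly in this population could pass unremarked. That ROC and concordance do not reveal a proportional error in survival is certain. The size of any error here is unknown: the groups, medians, exponential form and multipliers above are all assumptions, and the 21-point gap follows from the chosen doubling.

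A reader might go further and infer that a miscalibrated score would be declared fit for choosing treatment. The documents do not support this. They set no AUC target or other criterion for usability, and the aim speaks only of later informing the treatment approach. Nor do they give survival by tumour type: they give one overall range and say that lung cancer has the shortest survival among Caucasian cohorts.

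This is a change that should be made, not one that undermines the study. Survival is a secondary endpoint, but evaluating LENT in Chinese patients is a named aim, and without calibration that aim is only partly met.

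**What to change.** In the Statistical analysis section:

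1. State the original LENT score and its risk groups, the modification used, and whether the modification was fixed beforehand or derived from this cohort. Name the source of any predicted survival; the sponsor must supply it, as it is not in the documents.
2. For the original score, report observed Kaplan-Meier survival with 95% CI by risk group at 1, 3 and 6 months and at 14 weeks, beside the published survival for that group. Add an observed-to-expected ratio with 95% CI, and a calibration slope if the published predictions allow one.
3. If the modified score's cut-points or weights are derived in this cohort, report bootstrap optimism-corrected discrimination and calibration instead.
4. Base conclusions about the score on discrimination and calibration together.

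The cost is some wording and a small extra analysis of data already to be collected, with no extra patients, data items or procedures. The drawback is that the conclusion may be less favourable to the score.

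### The ROC analysis of the modified LENT score has no time horizon and no rule for censored patients, although follow-up is unequal; an AUC on status at cut-off would mostly understate a useful score, and overstatement needs score drift over calendar time

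*Combined protocol and SAP*

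**What the plan says.** All references are to the combined protocol and SAP.

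- **Statistical analysis.** The whole plan for the score is one sentence: it "will be investigated for risk stratification using the Kaplan Meier survival curve and Receiver Operating Characteristic curve analysis". The binary outcome for the ROC, its time point and the handling of patients still alive at last contact are not given. The same section plans a multivariable Cox model and linear regression for survival and pleural tapping.
- **Study investigations.** Retrospective cases are adults "with the diagnosis of malignant pleural effusion from 2010 and onwards". In addition, "patients newly diagnosed to have malignant pleural effusion, who are under the care of Department of Medicine, will also be prospectively recruited". No closing date, data cut-off or minimum follow-up appears. Retrospective patients are included "irrespective of their status at the study time (alive or dead").
- **Baseline characteristics.** Performance status, a component of the score, is among the variables that "will be collected at the start of study, and at the time of diagnosis of MPE". Which of the two values enters the score is not stated.
- **Outcomes.** Survival is a secondary endpoint with no time point.
- **Background.** It says that "the median survival rate ranges from 3 to 12 months". The only other survival threshold is 14 weeks, cited for the cost-effectiveness of indwelling catheters and not as an ROC horizon.

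**The concern.** An ordinary ROC curve needs one known yes/no outcome per patient. Survival under staggered entry does not supply that. Someone diagnosed years before the cut-off has had ample time to die, while a recent recruit has had weeks. If the analyst falls back on dead or alive at cut-off, the outcome reflects both prognosis and time observed, and the AUC answers no stated question such as death within 3 months.

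The stated aim is to evaluate LENT in Chinese patients so as to inform the treatment approach. An AUC with no horizon cannot be compared with other reports of the score or tied to a treatment decision. It could also shift for reasons unrelated to the score if the kind of patient enrolled changes over time.

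**Working it through.** The plan gives no sample size, event count or AUC, so there is no figure of its own to reproduce. The check asks how far an AUC on status at cut-off departs from an AUC at a fixed horizon.

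**Inputs.** From the documents: medians of 3 to 12 months and open entry from 2010. Assumed: exponential survival; three risk groups (low, middle, high) with medians 12, 6 and 3 months and shares 25%, 50% and 25%; uniform entry over 2, 6 or 10 years, with cut-off at the end of entry; no other loss to follow-up.

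**Formulas.** Probability of death by time t in a group with median m: 1 − 2^(−t/m). AUC = P(case in a higher group than control) + ½ P(same group).

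**Step 1: true AUC at 3 months.** Death probabilities are 0.159, 0.293 and 0.500.
- Weighted by the shares, cases split 0.128 / 0.471 / 0.402 and controls 0.305 / 0.513 / 0.181.
- AUC = 0.402 × (0.305 + 0.513) + 0.471 × 0.305 + ½ (0.128 × 0.305 + 0.471 × 0.513 + 0.402 × 0.181) = 0.329 + 0.144 + 0.177 = 0.65.
- The same steps at 6 months (0.293, 0.500, 0.750) give 0.67.

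**Step 2: status at cut-off, no drift.** Averaging over uniform follow-up gives the following.

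| Entry window | AUC on status | Below 3-month AUC (0.649) | Below 6-month AUC (0.671) |
|---|---|---|---|
| 2 years | 0.649 | 0.00 | 0.02 |
| 6 years | 0.642 | 0.01 | 0.03 |
| 10 years | 0.636 | 0.01 | 0.04 |

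A worthless score (all medians 6 months) gives 0.50 in every window. Staggered entry and censoring alone create no discrimination.

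**Step 3: a stronger score, no drift.** With a normal score, hazard ratio 2 per SD, and entry over 1 to 8 years, simulation of 1,000,000 patients per scenario gave about 0.70-0.71 on status. The true 6-month AUC was 0.78, 0.74 or 0.72 for medians of 3, 6 or 12 months. The largest gap is 0.779 − 0.697 = 0.08 (8 years, median 3 months).

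**Step 4: add calendar drift.**
- *Mild:* low-risk share rises from 20% to 30%, high-risk share falls from 30% to 20%. Worthless score: 0.52-0.53.
- *Strong:* low-risk share rises from 10% to 40%, high-risk share falls from 40% to 10%. Worthless score: 0.57-0.60; useful score: 0.71-0.72.
- *Worked case* (worthless, strong drift, 6 years): the dead split 0.234 / 0.500 / 0.266 and the living 0.364 / 0.500 / 0.136. AUC = 0.266 × 0.864 + 0.500 × 0.364 + ½ (0.234 × 0.364 + 0.250 + 0.266 × 0.136) = 0.230 + 0.182 + 0.186 = 0.60.
- *Opposite drift* mirrors this for a worthless score: 1 − 0.60 = 0.40.

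Strong drift corresponds to a correlation of about 0.245 between score and follow-up. With the score coded 0, 1, 2, its variance is 0.5. Its mean moves by 0.6 across the window, which contributes variance 0.36/12 = 0.03, and √(0.03/0.5) = 0.245. A normal worthless score at correlation 0.2 gave 0.585 (6 years, median 6 months), with p<0.05 in 36% of simulated studies at an assumed n of 300.

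**Step 5: the remedy.** Death by a fixed horizon, among patients whose potential follow-up reaches it, returns 0.65 at 3 months and 0.67 at 6 months for the useful score and 0.50 for the worthless one, even under strong drift. In the normal-score simulations at 6 months, p<0.05 occurred for the worthless score in 4-6% of studies.

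**The case against.** The strongest reply is that nothing says the ROC will use status at cut-off. Silence equally allows death by a fixed time or a time-dependent ROC. That stands: use of cut-off status is an inference, and what is certain is the missing outcome, horizon and censoring method. It does not dispose of the point, because the named method cannot be applied to censored survival until those are supplied.

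A reader might go further and infer that unequal follow-up by itself makes a worthless score look discriminating. It does not: without drift the AUC stays at 0.50. The documents report no change in case mix, and the drift scenarios are assumed. Drift is only plausible. Retrospective cases are hospital-wide while later ones come from one department with consent, and the timing of the performance status used in the score is open.

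A reader might also infer that a drainage ROC is planned in which early deaths count as no drainage, so that the score looks protective. No drainage ROC is specified; the score sentence sits beside the survival curve. With drainage hazards of 0.1, 0.2 or 0.4 per month, equal across the three groups, and unlimited follow-up, the AUC for ever being drained before death is 0.375. That is the correct value for that question and not a product of entry dates.

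Finally, Kaplan-Meier and Cox are also planned and accommodate non-informative censoring, and survival is a secondary endpoint. So it would be too much to say that a distorted AUC leads directly to a wrong conclusion about the score.

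**Conclusion.** The point holds, limited to the ROC for survival. The method named cannot deal with the unequal follow-up that the design creates, and a better one is readily available.

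If status at cut-off were used, the likely effect without drift is understatement: about 0.00-0.04 in the three-group set-up (0.00-0.03 for entry windows up to 6 years) and up to about 0.08 for a stronger score. Overstatement, including an AUC of 0.52-0.60 for a worthless score, requires higher scores among earlier entrants. The reverse pattern lowers the AUC.

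These sizes rest on exponential survival, uniform entry, administrative censoring only, and assumed entry windows, risk-group shares and drift. Only the 3-to-12-month range of medians comes from the documents. It is a modest defect that should be corrected before the analysis.

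**What to change.** In Statistical analysis, replace the ROC wording with: *time-dependent ROC for death at prespecified horizons (for example 3 and 6 months from MPE diagnosis), using a stated data cut-off date and either inverse-probability-of-censoring weights or restriction to patients whose potential follow-up is at least the horizon, plus a censoring-adjusted C-index, with bootstrap confidence intervals.*

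Three additions:
- If weights are used, make them conditional on entry period or cohort should the score drift, since marginal weights assume that censoring is independent of the score.
- Tabulate the score by entry year and by retrospective or prospective cohort, and state which performance-status measurement enters it.
- If a ROC for repeat drainage is also reported, treat death before drainage as a competing event at the same horizons and state who the controls are.

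The cost is a few sentences and standard software, with no new data. Weighting widens the intervals slightly; restriction loses the most recent entrants.
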